Increases in low-density lipoprotein-cholesterol (LDL-C) were observed in a pooled analysis of placebo-controlled 26-week studies with canagliflozin, increases in LDL-C relative to placebo were 4.4 mg/dL (0.11 mmol/L) and 8.2 mg/dL (0.21 mmol/L) at the 100-mg and 300-mg doses, respectively. Relative increases in Apolipoprotein B, non-high-density lipoprotein-cholesterol (HDL-C), and LDL particle number were approximately half as large as the rise in LDL-C. The changes in the CV risk profile with canagliflozin include reductions in systolic blood pressure and increases in LDL-C, both established CV risk factors, and validated as surrogate endpoints. Improvements in other endpoints associated with CV risk, but not established as surrogate endpoints for CV benefit, such as body weight, glycemic control, HDL-C, and triglycerides (TG) were also observed with canagliflozin. The cross-program CV meta-analysis (including results from the dedicated CV safety study) observed a hazard ratio of 0.91 for a pre-specified composite endpoint of CV death, non-fatal myocardial infarction (MI), non-fatal stroke, and hospitalized unstable angina (95% confidence interval [CI]: 0.68, 1.22), showing no signal for an increase in the CV risk.

In the adult Phase 3 program, treatment with canagliflozin was associated with a dose-dependent, reversible reduction in eGFR that was maximal at the first post-baseline visit and was either stable or attenuated with continued treatment. Analyses of eGFR post-discontinuation showed reversibility of the initial reductions in eGFR observed with canagliflozin. To assess the effects of canagliflozin on the progression of diabetic nephropathy, the proportion of subjects with categorical progression of albuminuria based upon the urinary albumin/creatinine ratio (ACR) was assessed in 4 Phase 3 studies (DIA3004, DIA3005, DIA3008, and DIA3009). Numerically greater mean and median reductions in urinary ACR with both doses of canagliflozin (100 mg and 300 mg) relative to placebo or comparator were observed in all 4 studies.

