## Management of double-blind study drug based on renal function

- Subjects who have undergone re-randomization and subsequently have a confirmed eGFR <60 mL/min/1.73m^2 will undergo down-titration (or mock down-titration) of blinded study drug at an unscheduled down-titration visit; only those who were up-titrated previously to the canagliflozin 300 mg dose will actually titrate down (in a blinded fashion via the IWRS). Subjects randomized to canagliflozin 100 mg or placebo will undergo a mock down-titration and continue their randomized treatment.
- If at any time during the study, a subject has a confirmed eGFR of <45 mL/min/1.73m^2, the subject must be discontinued from study drug as described in Section 10.2, Study Drug Treatment Premature Discontinuation, Reinstitution and Follow-up. Subjects discontinued from study drug and who do not withdraw consent will remain in the study and followed as described in Section 10.2. Study Drug Treatment Premature Discontinuation, Reinstitution, and Follow-up.
- Prior to down-titrating or discontinuing canagliflozin due to confirmed eGFR <60 mL/min/1.73m² or <45 mL/min/1.73m², respectively, a repeat determination should be performed within 1 week and study drug down-titrated or discontinued if the repeat determination confirms that the value still meet the criteria (unless a reversible acute cause is identified [eg, short-term illness or transient volume depletion] in which case an additional repeat determination can be performed after resolution of the illness).
- All subjects will receive a new medication kit assignment through the IWRS at the unscheduled down-titration visit. The investigator, or qualified assigned designee, will provide the subject with double-blind treatment medication with updated instructions on dosing and a new subject diary. The subject will be instructed to continue with the diet and exercise regimen and the completion of the study diary.

**Note:** Once a subject has up-titrated to canagliflozin 300 mg, down-titration is not allowed unless for confirmed eGFR <60 mL/min/1.73m^2. Therefore, if after up-titration to canagliflozin 300 mg a subject experiences recurrent hypoglycemia (ie, at least 2 episodes within a 7-day period), consideration should be given to down-titrate background AHA(s) such as insulin (or metformin).

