#### **Clinical Laboratory Tests**

Laboratory data will be summarized by type of laboratory test. Reference ranges and markedly abnormal results (to be specified in the SAP) will be referred to in the summary. Descriptive

statistics will be reported for each laboratory analyte at baseline and at each scheduled time point and for change from baseline.

Laboratory analyses will include percent change in lipids (ie, LDL-C, non-HDL-C and total cholesterol) from baseline at Week 26, and percent change in the ratio of LDL-C to HDL-C and non-HDL to LDL-C from baseline at Week 26, and change from baseline in bone turnover markers (serum osteocalcin and serum collagen type 1 CTx) and markers of calcium and phosphate homeostasis (calcium, magnesium, phosphate, PTH, 25-hydroxy Vitamin D, calcitonin; urinary excretion of calcium and phosphate). Additional laboratory parameters (listed in Attachment 7, Clinical Laboratory Tests) will also be analyzed.

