6.2. Clinical Laboratory Tests

Laboratory data will be summarized for each type of laboratory test listed in Attachment 3. Normal reference ranges for each test will be provided. Descriptive statistics (N, mean, SD, median, and range, as well as the 95% CI for the change from baseline) will be reported for each laboratory analyte at baseline and at each scheduled time point for absolute value and for change from baseline. The descriptive statistics will be presented based on measurements on study medication, including up to a maximum of 2 days after the last dose of study medication, as well as all measurements regardless of the time of the last dose of double-blind study drug. Summaries based on both standard units (SI) and conventional units will be provided.

The percentage of subjects with specific treatment-emergent laboratory values meeting predefined limit of change (PDLC) criteria will be summarized for these laboratory analytes. The 95% CI for the percentage difference between canagliflozin compared to placebo will be provided for each PDLC criterion which have at least 4 or more subjects in any treatment group; a corresponding listing will also be provided. The criteria for PDLC values are listed in Attachment 4.

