Central laboratory will report the estimated glomerular filtration rate (eGFR) at study visits when serum creatinine is measured as specified below:

- Estimated Glomerular Filtration Rate (eGFR)
 - eGFR will be calculated using Schwartz formula:
 - eGFR $(mL/min/1.73 \text{ m}^2) = (0.55 \times \text{height in cm}) / \text{serum creatinine in mg/dL for}$ girls from 10 to <18 years of age and boys from 10 to 12 years of age
 - $\circ~$ eGFR (mL/min/1.73 m²) = (0.70 \times height in cm) / serum creatinine in mg/dL for boys from 13 to <18 years of age

Laboratory Test	Parameter for ANY value and LAST value		
Chemistry			
	Absolute Value: >3X ULN		
ALT	Absolute Value: >5X ULN		
	Absolute Value: >8X ULN		
	Absolute Value: >3X ULN		
AST	Absolute Value: >5X ULN		
	Absolute Value: >8X ULN		
ALT >3X ULN and Tbili >2X	Composite: ALT >3X ULN and Tbili >2X ULN [with the Tbili elevation		
ULN	>2 X ULN within 30 days of the ALT elevation >3x ULN]		
AST >3X ULN and Tbili >2X	Composite: AST >3X ULN and Tbili >2X ULN [with the Tbili elevation		
ULN	>2 X ULN within 30 days of the AST elevation >3x ULN]		
Bilirubin	Composite: >ULN and >25% increase from BL		
	Absolute Value: >2X ULN		
Bicarbonate	Absolute Value: <16 mEq/L		
Calcium	Composite: >ULN and >10% increase from BL		
Magnesium	Composite: >ULN and >25% increase from BL		
Phosphorus Composite: >ULN and >25% increase from BL			
Potassium	Composite: <lln and="">15% decrease from BL</lln>		
	Composite: >ULN and >15% increase from BL		
	Absolute Value: $\geq 6.5 \text{ mEq/L}$		
Sodium	Composite: <lln and="" decrease="">5 mEq/L or more from BL</lln>		
	Composite: >ULN and increase>5 mEq/L or more from BL		
Urate	Composite: <lln and="">25% decrease from BL</lln>		
Hematology			
Hemoglobin	Change: $\geq 2 \text{ g/dL}$ decrease from BL		
	Change: $\geq 2 \text{ g/dL}$ increase from BL		
Vital signs			
Pulse	Absolute Value: ≤50 beats per minute		
	Absolute Value: ≥ 100 beats per minute		
Systolic Blood Pressure	Composite: ≥20 mm Hg decrease from BL and ≤90 mm Hg		
	Composite: ≥ 20 mm Hg increase from BL and ≥ 160 mm Hg		
Diastolic Blood Pressure	Composite: ≥ 15 mm Hg decrease from BL and ≤ 50 mm Hg		
	Composite: ≥15 mm Hg increase from BL and ≥100 mm Hg		

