Attachment 4: Criteria for Pre-defined Limit of Change (PDLC) and Abnormal Values

ULN = Upper Limit of Normal; LLN = Lower Limit of Normal; BL = Baseline

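### The SAP's limit-of-change list has no eGFR or creatinine row, so no planned analysis counts by arm the children who fall below the eGFR limits on which the protocol acts

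*SAP*

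**What the plan says.** Protocol 11.6 (Clinical Laboratory Tests) leaves the limits to the SAP: "Reference ranges and markedly abnormal results (to be specified in the SAP) will be referred to in the summary". SAP 6.2 takes this up: "The percentage of subjects with specific treatment-emergent laboratory values meeting predefined limit of change (PDLC) criteria will be summarized for these laboratory analytes", and "The criteria for PDLC values are listed in Attachment 4". A criterion met by at least four subjects in either group also gets a 95% confidence interval for the difference in percentages, and a listing.

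Attachment 4 covers ALT, AST, two composite liver criteria, bilirubin, bicarbonate, calcium, magnesium, phosphorus, potassium, sodium, urate, hemoglobin, pulse and blood pressure. It has no row for eGFR, creatinine or blood urea nitrogen.

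These analytes are nevertheless within the scope of SAP 6.2: "Laboratory data will be summarized for each type of laboratory test listed in Attachment 3". Attachment 3 lists creatinine and urea nitrogen, and states: "Central laboratory will report the estimated glomerular filtration rate (eGFR) at study visits when serum creatinine is measured as specified below".

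The protocol acts on eGFR. Under 9.1.4.3 (Management of double-blind study drug based on renal function), re-randomized subjects with a later confirmed eGFR below 60 "will undergo down-titration (or mock down-titration) of blinded study drug at an unscheduled down-titration visit". A confirmed eGFR below 45 leads to stopping study drug (9.1.4.3 and 10.2.1). Section 1.1.3 (Safety) describes the effect in adults: "treatment with canagliflozin was associated with a dose-dependent, reversible reduction in eGFR that was maximal at the first post-baseline visit".

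**The concern.** Overall safety and tolerability is a primary objective. A fall in eGFR is a described effect of the drug, and the protocol attaches two treatment actions to it. A safety reader will ask how many children in each arm went below 60, how many went below 45, and how many were down-titrated or stopped as a result. Following the SAP exactly leaves those numbers without a table. An imbalance between arms would have to be pieced together from visit-level minima, investigator-reported terms and discontinuation reasons, or found by a post hoc analysis after unblinding.

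**Working it through.** The plan states no figure to reproduce. The check is whether any planned analysis gives a count per arm at the two limits, and then how much an added row would yield.

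**1. Each planned analysis against the question: how many per arm fall below 60 or 45?**

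| Planned analysis | What it gives | What it lacks |
|---|---|---|
| PDLC percentages (SAP 6.2, Attachment 4) | Count, percentage and, from four subjects, a confidence interval | No eGFR or creatinine criterion |
| Descriptive laboratory statistics (SAP 6.2) | N, mean, SD, median and range, for value and change, at scheduled time points | The minimum shows that at least one subject crossed, not how many |
| Renal impairment/renal failure grouping (SAP 6.1.1, Attachment 2) | Subjects with reported terms such as a decreased filtration rate or increased creatinine | Needs an investigator report; applies no numeric limit |
| Adverse events by action taken (SAP 6.1) | Dose changes or stops attached to a reported event | Needs an investigator report |
| Disposition (SAP 4.2) | Reasons for stopping treatment | Names no eGFR category; misses subjects down-titrated but still on drug |

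Elsewhere the SAP uses eGFR 60 only for re-randomization (1.2, 1.5) and for the dose weights (5.4.2). The value 45 does not appear as an eGFR limit. No SAP table counts down-titrations.

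**2. Unscheduled results.** Serum chemistry after baseline is scheduled at Weeks 12, 26 and 52 and at a rescue visit (Time and Events Schedule). Confirmatory repeats and down-titration visits are unscheduled. SAP 2.1 restricts by-visit analyses to planned visits, with one visit per window. It names the PDLC analysis as an example of one that uses results from all visits. The table that would keep the unscheduled values is therefore the one without an eGFR row.

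**3. Why arm means do not stand in for a count.** Suppose 4 of 73 subjects fall by D units (both figures assumed). Their contribution to the arm's mean change is 4 × D / 73:
- D = 25: 100/73 = 1.4 units
- D = 60: 240/73 = 3.3 units

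**4. What a new row would yield.** With 73 per arm (SAP 1.4), the four-subject rule needs 4/73 = 5.5% in one arm. The documents give no crossing rate, so the true rate p is assumed and X ~ Binomial(73, p):

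| Assumed p | P(X ≥ 1) | P(X ≥ 4) |
|---|---|---|
| 1% | 0.52 | 0.006 |
| 2% | 0.77 | 0.059 |
| 5% | 0.98 | 0.50 |
| 10% | >0.999 | 0.94 |

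At low rates the row usually gives a small count without an interval.

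**5. Splitting by dose.** Under the plan's assumption that 50% are re-randomized, 73 × 0.5 / 2 is about 18 canagliflozin subjects per dose, too few for a useful comparison of rare crossings.

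**6. Confirmed crossings.** The protocol acts on confirmed values, but its repeat windows differ. The synopsis and 9.1.4.3 put the repeat within 1 week for both limits. Section 10.2.1 puts it at 7 to 14 days for the limit of 45. A confirmed count cannot be programmed until these passages are reconciled.

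**The case against.** The strongest reply is that renal safety is not left uncovered. A reader might infer from the missing row that the SAP reports only mean changes in eGFR, or that children who cross a limit would appear in no planned table. The documents support neither.

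- SAP 6.2 also gives the median and range for value and change, so each arm's lowest scheduled eGFR and largest scheduled fall are printed.
- Under protocol 9.8 the central laboratory sends alerts, and investigators must record clinically relevant laboratory changes as adverse events.
- Nephrotoxicity and acute kidney injury are adverse events of interest (protocol 12).
- The SAP analyzes a renal term grouping, summarizes events by action taken, applies its four-subject interval rule to adverse events, and summarizes discontinuation reasons.

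All of this stands. It shows that some crossings will surface, but none of these routes applies the limits of 60 or 45 or yields a number per arm.

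A reader might also infer that the SAP contradicts the protocol. It does not. Protocol 11.6 leaves markedly abnormal values to the SAP without naming analytes, and the SAP supplies a list. The omission is a choice of analytes.

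It is also fair that any crossing rate or size of fall is assumed, that a general eGFR fall would show in the arm summaries, and that a single value below a limit is not the confirmed event on which the protocol acts.

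**Conclusion.** The point holds in this limited form. Attachment 4 has no eGFR or creatinine criterion, no other planned analysis gives the number per arm below 60 or 45, and down-titrations are not tabulated. Renal safety is partly covered by ranges, reported events and discontinuation reasons, so this is a missing count rather than missing surveillance.

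The size in patients is unknown, because the documents give no crossing rate. At an assumed true rate of 1% to 2%, an arm of 73 would show at least one crossing in about 52% to 77% of trials and reach the four-subject rule in only about 1% to 6%. The benefit is mainly the count. The primary efficacy analysis is not affected. The change is worth making because safety is a primary objective, the effect is expected, the protocol acts on these limits, and the cost is small.

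**What to change.** Before unblinding:

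1. Add to Attachment 4, for any and last value and using all visits, treatment-emergent eGFR below 60 and below 45 mL/min/1.73m². Screening eGFR below 60 is an exclusion (protocol 4.2, criterion 9), so few if any subjects should start below either limit.
2. Add one change criterion: creatinine above the upper limit of normal with a rise of more than 25% from baseline, which follows the format of existing Attachment 4 rows, or another creatinine or eGFR change cut-off chosen by the sponsor.
3. Tabulate these by randomized arm (canagliflozin against placebo). A split by dose would be too thin to compare.
4. Tabulate actual and mock down-titrations, and discontinuations driven by eGFR, by arm.
5. Report confirmed crossings alongside single-value crossings once the sponsor has reconciled the repeat windows in the synopsis and 9.1.4.3 with the window in 10.2.1. This point takes no view on which is right.

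These are reporting criteria and change no clinical rule. The cost is a few table rows from data already collected. The downside is that the counts will probably be small and often come without an interval.

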6.3. Vital Signs and Physical Examination Findings

Descriptive statistics (N, mean, SD, median, and range) will be reported for SBP and DBP and pulse at each scheduled time point for absolute value and for change from baseline, including the 95% CI for the change from baseline. The descriptive statistics will be presented based on measurements on study medication, including up to a maximum of 2 days after the last dose of study medication, as well as all measurements regardless of the time of the last dose. The blood pressure measurements will be based on the average of the consecutive sitting blood pressure readings that were to be collected at each visit.

A treatment-emergent vital sign abnormality is defined as a change from baseline and subsequent post-baseline value that satisfies the criteria listed in the PDLC list (Attachment 4). For each vital sign parameter, the proportion of subjects with a treatment-emergent abnormality will be tabulated by treatment group.

7. PHARMACOKINETICS/PHARMACODYNAMICS

Concentrations will be reported for all subjects at all visits. Concentrations below the lower limit of quantification or missing will be labeled as such in the concentration database. Descriptive statistics, including arithmetic mean, SD, coefficient of variation, median, minimum, and maximum will be calculated and provided by treatment arm, and by treatment and background treatment. No population-based PK modeling is planned for this study.

REFERENCES

Crowe BJ (2009), Xia HA, Berlin JA, et al. Recommendations for safety planning, data collection, evaluation and reporting during drug, biologic and vaccine development: a report of the safety planning, evaluation, and reporting team. Clin Trials. 2009;6(5):430-440.

Hollander M (2013), Wolfe DA, Chichen E. Nonparametric Statistical Methods, Third edition. John Wiley and Sons, Inc., 2013.

Lu K (2008), Devan M, Liu G. Sample size determination for constrained longitudinal data analysis. Statistics in Medicine. 2008;28(4):679-699.

Proschan M (2011), Brittain E, Kammerman L. Minimize the use of minimization with unequal allocation. Biometrics. 2011;67(3):1135-1141.

Ratitch B (2013), O'Kelly M, Tosiello R. Missing data in clinical trials: from clinical assumptions to statistical analysis using pattern mixture models. Pharm Stat. 2013;12(6):337-347.

ATTACHMENTS

Attachment 1: Prestudy and Concomitant Medications Classified by ATC Code and/or Other Conditions

Antihyperglycemic Agents (AHA)

ATC Code starts with 'A10' (Drugs used in diabetes)

Insulin

ATC Code starts with 'A10A' (Insulins and analogues)

Biguanides

ATC Codes start with 'A10BA' (Biguanides); and/or 'A10BD' (combinations of oral blood glucose lowering drugs)

Antimicrobial Therapies

Antifungals: ATC Codes start with 'D01' (Antifungals for dermatological use), 'J02' (Antimycotics for systemic use), 'G01AF' (Imidazole derivatives), and 'G01AG' (Triazole derivatives). Antibacterials: ATC Codes start with 'D06' (Antibiotics and chemotherapeutics for dermatological use), 'J01' (Antibacterials for systemic use), 'G01AA' (Antibiotics), 'G01AB' (Arsenic compounds), 'G01AC' (Quinoline derivatives), 'G01AD' (Organic acids), and 'G01AE (Sulfonamides)'

Lipid-Altering Medications

ATC Codes start with 'C10'

Lipid modifying agents, plain ATC Codes start with 'C10A'

Lipid modifying agents, combinations ATC Codes start with 'C10B'

Attachment 2: List of Preferred Terms for Selected AEs of Interest

Vulvovaginal Candidiasis

Genital candidiasis; Genital infection; Genital infection female; Genital infection fungal; Urogenital infection fungal; Vaginal infection; Vaginal Inflammation; Vulvitis; Vulvovaginal candidiasis; Vulvovaginal mycotic infection; Vulvovaginitis.

Balanitis or Balanoposthitis

Acquired phimosis; Balanitis; Balanitis candida; Balanoposthitis; Balanoposthitis infective; Erosive balanitis; Gangrenous balanitis; Genital candidiasis; Genital infection; Genital infection fungal; Genital infection male; Penile infection; Phimosis; Posthitis.

Urinary Tract Infections

Bacterial pyelonephritis; Bacterial ureteritis; Bacterial urethritis; Bladder candidiasis; Cystitis; Cystitis bacterial; Cystitis escherichia; Cystitis gonococcal; Cystitis haemorrhagic; Cystitis interstitial; Cystitis klebsiella; Cystitis pseudomonal; Emphysematous cystitis; Emphysematous pyelonephritis; Escherichia urinary tract infection; Fungal cystitis; Funguria; Genitourinary tract infection; Kidney infection; Perinephric abscess; Pyelocystitis; Pyelonephritis; Pyelonephritis acute; Pyelonephritis chronic; Pyelonephritis fungal; Pyelonephritis mycoplasmal; Pyelonephritis viral; Pyonephrosis; Renal abscess; Renal cyst infection; Streptococcal urinary tract infection; Ureter abscess; Ureteritis; Urethral abscess; Urethral carbuncle; Urethral stricture post infection; Urinary bladder abscess; Urinary tract abscess; Urinary tract infection; Urinary tract infection pseudomonal; Urinary tract infection staphylococcal; Urosepsis; Urethritis; Urinary tract infection staphylococcal; Urosepsis; Urethritis; Urethrit

Volume Depletion

Blood pressure decreased; Blood pressure orthostatic decreased; Dehydration; Diastolic hypotension; Dizziness postural; Hypotension; Hypovolaemia; Hypovolemic shock; Orthostatic hypotension; Orthostatic intolerance; Postural orthostatic tachycardia syndrome; Presyncope; Shock; Shock symptom; Syncope; Urine output decreased.

Renal Impairment/Renal Failure

Acute kidney injury; Acute phosphate nephropathy; Acute prerenal failure; Anuria; Azotaemia; Blood creatinine increased; Blood urea increased; Continuous haemodiafiltration; Dialysis; Glomerular filtration rate decreased; Haemodialysis; Haemofiltration; Hypercreatinaemia; Neonatal anuria; Nephritis; Nephropathy toxic; Oliguria; Peritoneal dialysis; Prerenal failure; Renal failure; Renal failure acute; Renal failure neonatal; Renal impairment; Renal impairment neonatal.

Hypersensitivity

Anaphylactic reaction; Anaphylactic shock; Anaphylactoid reaction; Anaphylactoid shock; Angioedema; Laryngeal oedema; Laryngotracheal oedema; Oropharyngeal swelling; Pharyngeal oedema; Rash; Rash erythematous; Rash generalized; Rash generalized; Rash macular; Rash maculopapular; Rash maculo-papular; Rash papular; Rash pruritic; Rash pustular; Rash vesicular; Small bowel angioedema; Swollen tongue; Tongue oedema; Urticaria.

Venous Thromboembolic Event

Deep vein thrombosis; Deep vein thrombosis postoperative; Embolism venous; Iliac vein occlusion; Inferior vena cava syndrome; Inferior vena caval occlusion; Jugular vein occlusion; Mesenteric vein thrombosis; Mesenteric venous occlusion; Obstructive shock; Portosplenomesenteric venous thrombosis; Post procedural pulmonary embolism; Postpartum venous thrombosis; Pulmonary embolism; Pulmonary infarction; Pulmonary microemboli; Pulmonary oil microembolism; Pulmonary thrombosis; Renal vein embolism; Renal vein occlusion; Subclavian vein thrombosis; Vascular occlusion; Venous thrombosis; Venous thrombosis in pregnancy; Venous thrombosis limb; Visceral venous thrombosis.

Photosensitivity

Actinic elastosis; Actinic prurigo; Administration site photosensitivity reaction; Application site photosensitivity reaction; Chronic actinic dermatitis; Hartnup disease; Implant site photosensitivity; Infusion site photosensitivity reaction; Injection site photosensitivity reaction; Juvenile spring eruption; Medical device site photosensitivity reaction; Photodermatosis; Photokeratitis; Photoonycholysis; Photosensitivity reaction; Polymorphic light eruption; Solar dermatitis; Solar urticaria; Sunburn; Vaccination site photosensitivity.

Hepatic Injury

Acute graft versus host disease in liver; Acute hepatic failure; Acute yellow liver atrophy; Allergic hepatitis; Ammonia increased; Ascites; Asterixis; Autoimmune hepatitis; Bacterascites; Biliary ascites; Biliary cirrhosis; Biliary cirrhosis primary; Biliary fibrosis; Bilirubin excretion disorder; Biopsy liver abnormal; Child-Pugh-Turcotte score increased; Cholaemia; Cholestasis; Cholestatic liver injury; Cholestatic pruritus; Chronic graft versus host disease in liver; Chronic hepatic failure; Chronic hepatitis; Coma hepatic; Cryptogenic cirrhosis; Diabetic hepatopathy; Drug-induced liver injury; Duodenal varices; Focal nodular hyperplasia; Gallbladder varices; Gastric varices; Gastric varices haemorrhage; Graft versus host disease in liver; Haemangioma of liver; Haemorrhagic ascites; Haemorrhagic hepatic cyst; Hepatectomy; Hepatic adenoma; Hepatic atrophy; Hepatic calcification; Hepatic cirrhosis; Hepatic cyst; Hepatic cyst ruptured; Hepatic encephalopathy; Hepatic encephalopathy prophylaxis; Hepatic failure; Hepatic fibrosis; Hepatic fibrosis marker abnormal; Hepatic haemangioma rupture; Hepatic hydrothorax; Hepatic infiltration eosinophilic; Hepatic lesion; Hepatic necrosis; Hepatic steatosis; Hepatitis; Hepatitis acute; Hepatitis cholestatic; Hepatitis chronic active; Hepatitis chronic persistent; Hepatitis fulminant; Hepatitis toxic; Hepatobiliary disease; Hepatocellular foamy cell syndrome; Hepatocellular injury; Hepatopulmonary syndrome; Hepatorenal failure; Hepatorenal syndrome; Hepatotoxicity; Hyperbilirubinaemia; Icterus index increased; Intestinal varices; Ischaemic hepatitis; Jaundice;

Jaundice cholestatic; Jaundice hepatocellular; Liver and small intestine transplant; Liver disorder; Liver injury; Lupoid hepatic cirrhosis; Lupus hepatitis; Mixed liver injury; Nodular regenerative hyperplasia; Non-alcoholic steatohepatitis; Non-cirrhotic portal hypertension; Ocular icterus; Oedema due to hepatic disease; Oesophageal varices haemorrhage; Parenteral nutrition associated liver disease; Peripancreatic varices; Periportal oedema; Portal hypertension; Portal hypertensive enteropathy; Portal hypertensive gastropathy; Portal triaditis; Portal vein cavernous; transformation; Portal vein dilatation; Portopulmonary hypertension; Radiation hepatitis; Renal and liver transplant; Retrograde portal vein flow; Reye's syndrome; Reynold's syndrome; Splenic varices; Splenic varices haemorrhage; Subacute hepatic failure; Varices oesophageal; Varicose veins of abdominal wall.

Malignancy Renal Cell Cancer

Clear cell renal cell carcinoma, Clear cell sarcoma of the kidney, Denys-Drash syndrome, Hereditary leiomyomatosis renal cell carcinoma, Hereditary papillary renal carcinoma, Metastatic renal cell carcinoma, Nephroblastoma, Non-renal cell carcinoma of kidney, Papillary renal cell carcinoma, Renal cancer, Renal cancer metastatic, Renal cancer recurrent, Renal cancer stage I, Renal cancer stage II, Renal cancer stage III, Renal cancer stage IV, Renal cell carcinoma, Renal cell carcinoma recurrent, Renal cell carcinoma stage I, Renal cell carcinoma stage II, Renal cell carcinoma stage III, Renal cell carcinoma stage IV, Rhabdoid tumour of the kidney.

Malignancy Bladder Cancer

Bladder adenocarcinoma recurrent, Bladder adenocarcinoma stage 0, Bladder adenocarcinoma stage I, Bladder adenocarcinoma stage II, Bladder adenocarcinoma stage III, Bladder adenocarcinoma stage IV, Bladder adenocarcinoma stage unspecified, Bladder cancer, Bladder cancer recurrent, Bladder cancer stage 0, with cancer in situ, Bladder cancer stage 0, without cancer in situ, Bladder cancer stage I, with cancer in situ, Bladder cancer stage 0, without cancer in situ, Bladder cancer stage II, Bladder cancer stage III, Bladder cancer stage II, Bladder cancer stage III, Bladder cancer stage II, Bladder cancer stage II, Bladder cancer stage II, Bladder squamous cell carcinoma stage II, Bladder squamous cell carcinoma stage II, Bladder squamous cell carcinoma stage III, Bladder squamous cell carcinoma stage IV, Bladder transitional cell carcinoma stage IV, Bladder transitional cell carcinoma stage I, Bladder transitional cell carcinoma stage II, Bl

Malignancy Phaeochromocytoma

Phaeochromocytoma, Phaeochromocytoma crisis, Phaeochromocytoma excision, Phaeochromocytoma malignant.

Malignancy Breast Cancer

Apocrine breast carcinoma, Breast angiosarcoma, Breast angiosarcoma metastatic, Breast cancer, Breast cancer female, Breast cancer in situ, Breast cancer male, Breast cancer metastatic, Breast

cancer recurrent, Breast cancer stage I, Breast cancer stage II, Breast cancer stage III, Breast cancer stage IV, Breast neoplasm, Breast sarcoma, Breast sarcoma metastatic, Breast sarcoma recurrent, Contralateral breast cancer, HER-2 positive breast cancer, Hormone refractory breast cancer, Inflammatory carcinoma of breast recurrent, Inflammatory carcinoma of breast stage IV, Inflammatory carcinoma of the breast, Intraductal papillary breast neoplasm, Intraductal proliferative breast lesion, Invasive breast carcinoma, Invasive ductal breast carcinoma, Invasive lobular breast carcinoma, Invasive papillary breast carcinoma in situ, Malignant nipple neoplasm, Malignant nipple neoplasm female, Malignant nipple neoplasm male, Medullary carcinoma of breast, Metaplastic breast carcinoma, Neuroendocrine breast tumour, Nipple neoplasm, Oestrogen receptor positive breast cancer, Paget's disease of nipple, Phyllodes tumour, Triple negative breast cancer, Tubular breast carcinoma.

Malignancy Testicular

Benign neoplasm of testis, Leydig cell tumour of the testis, Sertoli cell testicular tumour, Spermatocytic seminoma, Testicle adenoma, Testicular cancer metastatic, Testicular neoplasm, Testicular papilloma, Testis cancer.

